### Design

For Aim 1, we plan to recruit 460 study participants from 19 memory care facilities. For the purpose of this study, facilities will include Skilled Nursing Facilities (SNFs), or equivalent. Aim 1 will be a randomized controlled study using a waitlist control group. The randomization will occur at the individual (resident) level within each facility to control for variations at each facility in terms of facility size, facility administration, and staff training. During the first 6 months, n=230 will receive the intervention (SafelyYou Guardian, i.e. real-time alarms through a phone call from the HIL to the facility, front line staff intervention, and OT review), and n=230 will not receive the intervention. This design is the most rigorous way to test the intervention against the control: the randomization allows for control of confounding variables and has been previously used in the evaluation of medications, non-pharmacological, and mobile electronic interventions (where use of placebo treatment and blinding is not feasible) [87-89]. Previous work used a baseline as control, allowing possible confounding variables. As we recognize that 50% of the interested participants will not receive the intervention, those residents will be offered the intervention for a 6-month extension period (in order to accomplish Aim 2). This is the best compromise between the need for a rigorous randomized controlled trial vs. ethical responsibility to maximize benefit to each study participant.

For Aim #2, we will measure response times to each fall and the amount of time a resident spends on the ground after each fall. We intend to include all 460 participants' data from Aim #1. These will be participants who receive the initial intervention (n=230) and the additional participants who are on the waitlist control group who will receive the intervention in the second 6month period. The design for Aim #2 is observational in nature. The significance is that a large cohort of video data about the naturalistic progression of falls in residents with dementia has never been conducted to our knowledge. We will determine if the two time variables (time to fall discovery by staff and time spent on the ground after a fall, controlling

for baseline participant characteristics – i.e., demographics and medical conditions) and facility size, will predict need for ER visits or hospitalizations.

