Data analysis: For aims 1, statistical analyses to address baseline comparison: Subjects' baseline characteristics (demographics and medical conditions) will be compared between the intervention and control groups using 2-sample t-tests (or appropriate nonparametric tests if the assumption of normality appears to be violated) and chi-square tests for continuous and categorical variables. Descriptive statistics will be used (means, frequencies, standard deviations, 95% confidence intervals) for all variables. We will examine the Aim #1a outcomes using a Poisson mixed-effects model to account for the nesting of outcomes within centers. We will account for baseline measures of resident activation and health status and resident demographics to statistically adjust for baseline imbalances, reduce residual intra-cluster correlation and improve the precision of estimated effects. Power analyses were performed via a simulation study in R version 3.4. and the lme4 package. We used 3 months of pilot data to guide and set assumptions for the data generating process. Based off initial data, we assumed centers ranged in size from 25-45 participants, and that roughly 30% of participants at each site would consent to the trial. Of those who consent, 50% will be randomized to the intervention. We fit the pilot data to a Poisson mixed effects model to obtain an estimate of the average monthly fall rate (0.49) as well as the between cluster variation in log fall rate ( $\sigma_{\text{twn}} = 0.467$ ). We generated 1000 sample data sets assuming different effect sizes (40%, 30%, 25% reduction in falls) and calculated the power obtained to detect this improvement due to intervention, as a function of the number of centers.

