Following the sample size for a time-averaged response methodology laid out in Fitzmaurice et al., we adjusted the total number of centers needed by a factor related to the number of observed months, anticipated participants per center (30% of 35 participants per center with 10% dropout) and the correlation between measurement months. The dropout rate was roughly at ~1% per month so a 10% dropout over 6 months is a conservative estimate. We assumed an extremely conservative estimate of the correlation between time points (months) of 0.8 and 6 months of follow-up. Reproducible R code is available at <https://github.com/[name]/>. We estimate that a total sample size of 460 ( $n=230/\text{arm}$ ) out of 19 facilities will be needed for a power of 80% to detect a 30% reduction in falls in the intervention group vs. control. Our approach of focusing on estimation and uncertainty and accepting the sample size collected for the main study, is congruent with experts' recommendations stating that the purpose of economic evaluation is not hypothesis testing; given there is no hypothesis testing, there is no requirement for a separate sample size calculation. For Aim 2, we will use similar descriptive statistics as described in Aim 1. For Aim 3, We will use a multivariate regression model to examine predictors of the main outcome, ER visits and hospitalizations (binary variable), using time to fall discovery by staff and time spent on the ground as the main predictors while controlling for baseline participant characteristics and facility characteristics.

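### The observational time-to-transfer model in Aim 3 has no facility effect, so between-facility differences can appear as an effect of response time

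*Combined protocol and SAP*

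**What the plan says.** Two places describe the model that links response time to transfer, and they differ.

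- Design, Aim #2 paragraph: the two time variables "and facility size, will predict need for ER visits or hospitalizations". The control set given there is "for baseline participant characteristics – i.e., demographics and medical conditions". Facility size is the only facility variable named.
- Data analysis paragraph under Clinical outcomes, Aim 3: "We will use a multivariate regression model to examine predictors of the main outcome, ER visits and hospitalizations (binary variable"), with the two times as main predictors, "while controlling for baseline participant characteristics and facility characteristics". The facility characteristics are not listed.

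Three other statements bear on this. The Design section explains that randomisation is done within facility "to control for variations at each facility in terms of facility size, facility administration, and staff training". It says of the time analysis: "The design for Aim #2 is observational in nature". For Aim 1 the analysis is a "Poisson mixed-effects model to account for the nesting of outcomes within centers"; nothing comparable is stated for the Aim 3 regression. The variables listed under Data collection describe residents and falls, and no facility-level variable is among them.

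**The concern.** Randomisation within facility protects the comparison of arms. It does not protect a comparison of falls with long and short response times, because time is observed and is available only for monitored residents. A facility's administration and staff training could influence how quickly staff reach a resident, and also whether the resident is sent to the ER. If so, pooling falls over 19 facilities puts that difference between facilities into the time coefficient. Size is at best a partial stand-in, and administration and training cannot be adjusted for if nobody records them.

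There is a second, separate problem. Falls in one facility share its transfer practice. A regression that treats them as independent understates the standard error of any predictor that also varies by facility.

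At stake is the second half of Hypothesis 3, that fewer ER visits and hospitalizations go with less time on the ground. This regression is the only model described for that link. A positive result could not separate faster response from facilities that both respond faster and transfer less.

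**Working it through.** The plan gives no sample size, power or effect for this model, so there is no figure to reproduce. The 460 participants and 80% power belong to Aim 1. The check has two parts: reading the text, and an illustration of how large the problem could be.

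**Text.** Facility differences the plan recognises: size, administration, staff training. Facility terms in the time model: size (Design) or an unlisted set (Data analysis). Facility effect or clustering term: none stated. Facility variables listed as collected: none.

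**Scale, from the documents.** 460 residents × 0.49 falls per month × 6 months = 1,352 falls, or 1,352 × 0.7 = 947 after the 30% reduction assumed for Aim 1. The illustration uses 19 × 50 = 950 falls. The fall is taken as the unit because times are measured per fall; the plan does not say so for this model.

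**Assumed, not in the documents.** About 20% of falls transferred; within-facility SD of log time 0.8; facility SDs of 0.4 (log time) and 0.6 (logit transfer), then both halved; facility-level correlation ρ between the two. Time has no effect within any facility.

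**Hand approximation.** Pooling falls gives a slope on log time of about

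β ≈ ρ × SD(time) × SD(transfer) / [SD(time)² + 0.8²]

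- SDs 0.4/0.6: β ≈ ρ × 0.24 / (0.16 + 0.64) = 0.300ρ
- SDs 0.2/0.3: β ≈ ρ × 0.06 / (0.04 + 0.64) = 0.088ρ

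The odds ratio per doubling is exp(0.693β). For example, at 0.4/0.6 and ρ = 0.5 it is exp(0.693 × 0.150) = 1.11.

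**Simulation**, 400 data sets per setting, logistic model adjusting for facility size only. Ranges are over repeated runs.

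| Facility SDs | ρ | Odds ratio by hand | Simulated odds ratio | False positives at 5% |
|---|---|---|---|---|
| 0.4/0.6 | 0.3 | 1.06 | 1.05–1.06 | 18–21% |
| 0.4/0.6 | 0.5 | 1.11 | 1.09 | 29–32% |
| 0.4/0.6 | 0.7 | 1.16 | 1.13–1.14 | 50–53% |
| 0.2/0.3 | 0.3 | 1.02 | 1.02 | 6.5% |
| 0.2/0.3 | 0.5 | 1.03 | 1.02 | 4% |
| 0.2/0.3 | 0.7 | 1.04 | 1.04 | 9% |

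A repeat of the halved-SD setting gave 7% to 9%. The Monte Carlo standard error is √(0.05 × 0.95 / 400) = 1.1 points near 5% and √(0.5 × 0.5 / 400) = 2.5 points near 50%.

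**With facility fixed effects**, at 0.4/0.6: odds ratio 0.99 to 1.01, false positives 5% to 8%.

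**Separating the two problems**, at 0.4/0.6. With ρ = 0 there is no confounding, yet the size-only model still rejects in about 10% to 13% of runs; cluster-robust errors bring that to 6%. With ρ = 0.3, 0.5 and 0.7, cluster-robust errors still leave 11%, 18% and 39%. Correcting the standard error is therefore not enough, because the estimate itself is shifted.

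**Second set of assumptions.** 19 × 60 = 1,140 falls, 300 runs per setting, facility SD in logit transfer 0.3 to 0.8, intra-facility correlation of time 0.1 to 0.3. For ρ of 0.3 to 0.6 the size-only model gave odds ratios of 1.03 to 1.24 per SD of time and rejected in 9% to 73% of runs. For ρ = 0 it gave 0.99 to 1.01 and 6% to 21%. Fixed effects over all settings gave 0.99 to 1.01 and 3% to 8%.

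**The case against.** A reader of the Design sentence might infer that the plan adjusts for facility size and nothing else. The documents do not support that. The Data analysis paragraph is the analysis text for Aim 3, and its facility characteristics are plural and not confined to size. Participant characteristics are adjusted for in both places. As punctuated, the Design sentence may even make size a predictor alongside the times. This stands, and it limits the point: the two statements disagree, the characteristics are undefined, and no facility effect is stated. It does not remove the point, because an unlisted and uncollected set of variables cannot be relied on to absorb administration and training.

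A reader might also infer that Aim 3 as a whole is compromised. It is not. Hypothesis 3 leads with a comparison against control, which is randomised within facility; the time association comes second and is described as observational.

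The confounding path is partly assumed. No section says that transfer practice differs by facility. The Risk/Benefit Assessment says the system should help staff decide about ER transfer, which makes staff practice a plausible influence but is not evidence that it varies. Time to discovery may also depend less on the facility than time on the ground does: the Aims define it as time to staff notification, and Data collection describes a call from the human in the loop. Clinical outcomes ties it to staff intervention, so some facility component remains. One facility SD for both times is a simplification.

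The size is also sensitive to the inputs. Halving both facility SDs brings false positives close to nominal.

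It is tempting to add that shift should be in the model, since the time of each fall is recorded. The documents describe no shift or night-staffing pattern and the check did not test it, so it forms no part of this point.

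**Conclusion.** The concern holds for the secondary, observational time-to-transfer analysis. As described, the model cannot distinguish a within-facility effect of response time from differences between facilities, and it makes no allowance for clustering.

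How much this matters cannot be derived from the documents. Under the assumptions shown, it runs from negligible (odds ratio about 1.02 per doubling, false positives near 5%) to serious (about 1.14, false positives about 50%). The conclusion rests on facilities differing in both response time and transfer practice, with the two correlated. The plan's own account of facility differences makes this plausible without establishing it. If the correlation is zero, only the clustering problem remains.

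**What to change.** 1. Reconcile the Design and Data analysis statements, list the covariates and state the unit of analysis.
2. Estimate the time effect within facility, by logistic regression with facility fixed effects or conditional on facility. This needs no new data, since each resident's facility is known.
3. If facility size is to remain a predictor, use facility-mean-centred time together with the facility mean of time, and a facility random intercept. The centred term carries the within-facility effect and size stays estimable.
4. Allow for repeated falls in the same resident.

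The cost of fixed effects is 19 − 1 = 18 degrees of freedom out of roughly 950 to 1,350 falls. Facilities with no transfers contribute no information, and facility size is no longer estimated. The Aim 1 analysis and the randomised comparison of ER visits and hospitalizations need no change on this account.

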For aim #3, we will ascertain the occurrence of fall in the intervention group by doing follow-up case review of each detected fall. For the control group, we perform biweekly check with facility staff and family regarding knowledge and documentation of any falls. For falls in both the intervention and control group, we will additional collected data regarding occurrence of ED visit and hospitalization days. We will also include occurrence (or absence) of any operations, intensive care unit stays, and other medical procedures. We will also collect mortality data.

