**Privacy and security safeguards.** Privacy: A common concern with any video-based monitoring system is privacy. Through the series of pilots discussed previously and shown in Fig. 3, we have systematically validated the privacy/safety tradeoffs for residents, families, staff, owners, and operators of memory care facilities. Pilot 2 demonstrated at small scale (one facility, 10 residents) that the industry would be receptive to video-based fall detection and prevention. Pilots 3 and 4 confirmed the approach with 11 facilities and 87 residents while demonstrating significant positive outcomes including 37% reduction in use of EMS for falls and 38% reduction in total falls. We now have paid commitments for 480 beds and ongoing discussions regarding expansion within the networks from the Phase I facilities, validating the benefits outweigh potential privacy and legal concerns for a number of families and providers. The combined benefits of (1) reduced time on the ground due to real-time intervention of front line staff, (2) immediate assessment of severity when a resident is found on the ground without witness, and (3) reduced likelihood of future falls through intervention of OT make our commercial approach viable. The key point is that as dementia progresses, the need to keep a loved one safe often surpasses concerns regarding their privacy. The benefits provided by SafelyYou in terms of reduced falls and ED visits have surpassed the concerns for the majority in memory care facilities where 85%-90% opt-in for the system. For more information from families and care staff validating these numbers and sentiments, please see letters from [name], [name], [name], [name], and video:

<https://youtu.be/ThUsBVOAJ3A>. This video was made with explicit permission from all residents/families for the purposes of promoting our work and supporting further recruitment. During pilots 2, 3 and 4, no live video was available and video was recorded whenever motion was detected. For new customers signing up for the system and for the Phase II clinical trial, no live video access is available and videos that do not contain a detected fall are not kept after 60 seconds as enabled by the highly accurate fall detection system developed in Phase I. We have never placed video cameras in bathrooms and will not for the Phase II clinical trial. In our 11 partner facilities, the Phase I showed that only 5-10% of

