#### **Data collection:**

Demographic and clinical data set: We collect demographic data including age, gender, race/ethnicity, primary clinical diagnoses for SNF stay with specific focus on dementia subtype, most recent orthopedic surgery (<3 months) or reason for hospitalization, chronic medical conditions (top 3), and baseline medications (number of medications). Beyond the data collected from the video, data specific to the falls is collected either by direct extraction from the platform or from incident reports kept by facilities as (State regulations require facility track and file incident reports for all known falls). For the control population, the time of unwitnessed falls is unknown, but the number of falls and ER visits is collected from the existing facility incident reports. For the population equipped with SafelyYou Guardian, we will have direct access to the time of the fall, the time it took the HIL to verify the fall and call the facility, and the time on the ground. Note that for the residents with SafelyYou Guardian, we expect these values to be in increments of minutes.

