#### Clinical outcomes.

For Aim #1, the primary outcomes are the number of falls detected by facilities using the adverse incident reporting system as per routine facility protocol. While use of video detected falls will be used in the intervention group to assist with prevention of future falls, we will not use this as the actual outcome measure: is not the standard-of-care, and the control group will not have video recorded outcomes. There is a bias for detecting falls using video since existing fall reporting systems do not capture falls which staff do not know about (e.g., when a resident is able to get back in bed after a fall). Staff-detected falls which automatically trigger adverse incident reporting is the “real-world” outcome measure and current stand-of-care. Thus, outcomes will differ by facility (each facility has different adverse incident reporting operations and implementation, hence the randomization at each facility will adjust for such variables).

Aim #2 will be a naturalistic observation of SafelyYou Guardian with HIL for 6 months. Specifically, for all the facilities, the use of the SafelyYou Guardian enables direct notification of falls to front-line staff in the facilities, by intervention of the HIL. We can directly measure time on the ground for the residents as follows: (1) The time of the fall is recorded by

SafelyYou Guardian (which detected it); (2) The time of intervention of the front-line staff is logged by the staff after finding the residents on the ground. This means that for the population with treatment, we can directly measure the time of fall discovery (successful call leading to front line staff intervention), and time on the ground (since time of the intervention is logged by the facility). This is because time on the ground for monitored residents can be measured precisely by video recording. Reduction of the time on the ground can be computed given the difference between the two.

Aim #3 will include number of ER visits and number of hospitalizations. We will obtain information about resident demographics, medical comorbidities, emergency room visits, and hospitalization data by asking the study participant legal representatives. In addition, we will have participant / participant Durable Power of Attorney complete HIPAA consent forms for release of medical records when indicated if the details of data are not available.

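### Hypothesis 3 compares ED visits and hospitalizations with control, but the only Aim 3 model has no arm term and cannot use control data; the source of the Aim 3 count is also not fixed across arms.

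*Combined protocol and SAP*

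**What the plan says.** **Hypothesis and model.** Aims & Hypotheses states Hypothesis 3 as a comparison with control on ED visits and hospitalizations, and adds that their association with falls and ground time will be reviewed. Data analysis gives Aim 3 one model: a multivariate regression with ER visits and hospitalizations as a binary outcome, the two time variables as main predictors, and baseline and facility covariates. Arm is not listed. The Poisson mixed model in the same section is assigned to the Aim 1 outcome. Clinical outcomes defines the Aim 3 outcomes as numbers of ER visits and of hospitalizations.

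**How events are found.** For Aim 3, Design says "we will ascertain the occurrence of fall in the intervention group by doing follow-up case review of each detected fall". It continues: "For the control group, we perform biweekly check with facility staff and family regarding knowledge and documentation of any falls". It then ties utilisation to those falls: "For falls in both the intervention and control group, we will additional collected data regarding occurrence of ED visit and hospitalization days". Data collection says of the control population that "the number of falls and ER visits is collected from the existing facility incident reports". Clinical outcomes adds a route that names no arm, obtaining ER and "hospitalization data by asking the study participant legal representatives", with medical-records release when details are lacking.

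**Other events.** Design also says "We will also include occurrence (or absence) of any operations, intensive care unit stays, and other medical procedures" and "We will also collect mortality data".

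**The concern.** A randomised hypothesis needs an estimator of the randomised contrast, and Aim 3 has none. If the plan is followed as written, the trial reports how ED use varies with discovery time and ground time among monitored residents. That is an observational question. Any comparison of ED visits and hospitalizations by arm would have to be devised later, with the choice between counts and a binary outcome still open.

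The second issue is what gets counted. If ED visits enter the data through a detected fall in one arm and through a staff and family check in the other, a difference between arms could partly reflect how events were found. Randomisation within facility balances the residents; it does not balance a measurement route that depends on arm. Clinical outcomes recognises this problem for Aim 1 and settles it by using facility incident reports in both arms. Aim 3 has no equivalent rule.

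**Working it through.** **1. Can the stated model give the contrast?**

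| Needed for Hypothesis 3 | What the plan gives | Where |
|---|---|---|
| Arm effect | No arm term listed | Data analysis |
| Predictors observed in both arms | Ground time not measurable in controls | Aims & Hypotheses, Aim 2 |
| | Time of controls' unwitnessed falls unknown | Data collection |
| One outcome definition | Count in one section, binary in the other | Clinical outcomes; Data analysis |

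Adding an arm term to this model would not rescue it. Controls lack a main predictor during the controlled period, and a resident who does not fall has no ground time in either arm. The model can be fitted only to falls in monitored residents. Design already describes it that way: predicting ER or hospital need from the two times appears under Aim 2, which is called observational.

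**2. Which source defines the Aim 3 count?**

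| Source | Intervention | Control |
|---|---|---|
| Case review of detected falls (Design) | Yes | No |
| Biweekly staff and family check (Design) | Not stated | Yes |
| Incident reports (Data collection) | Possible source of fall data | Named source of falls and ER visits |
| Legal representatives, records if needed (Clinical outcomes) | Arm not named | Arm not named |

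The last row could supply a common count. No section says that it does, or on what schedule.

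**3. What precision could an arm comparison have?** The plan states no ED rate and no power for Aim 3, so there is no figure to reproduce. What follows is illustrative.

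Inputs from Data analysis: 0.49 falls per month, 6 months, 230 per arm, 30% fewer falls. Assumptions: 20% of falls lead to an ED visit; 30% to 70% of all ED visits are fall-related; visits per fall are the same in both arms; non-fall visits are unaffected; no dropout.

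- Control falls: 0.49 x 6 x 230 = 676. Fall-related control visits: 0.20 x 676 = 135.
- All-cause ratio with fall-related share f: 0.70f + (1 - f). At f = 0.3 it is 0.91; at f = 0.7 it is 0.79.
- All-cause control visits, 135/f: about 451 and 193. Intervention visits: 451 x 0.91 = 410 and 193 x 0.79 = 153.
- 95% CI: ratio x exp(±1.96 x sqrt(phi x (1/control + 1/intervention))), where phi is variance divided by mean.

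| f | Ratio | phi = 1 (Poisson) | phi = 2 |
|---|---|---|---|
| 0.3 | 0.91 | 0.80-1.04 | 0.75-1.10 |
| 0.7 | 0.79 | 0.64-0.98 | 0.59-1.07 |

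If 40% of falls lead to an ED visit, all counts double. The Poisson intervals become 0.83-1.00 and 0.68-0.92, and the phi = 2 intervals equal the phi = 1 row values above. Dropout would widen all of them somewhat.

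**The case against.** The best defence concerns ascertainment. The word 'detected' is not defined for Aim 3, and Clinical outcomes also uses it for falls found by facility staff. Data collection says state rules require incident reports for all known falls. A fall that sends a resident to the ED will usually be known to staff, and the enquiry to legal representatives, with records release, names no arm. Together these could remove most or all of the difference. This stands. What survives is narrower: the plan does not say which source governs.

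A reader might infer a quantified bias, because cameras are in bedrooms only and "the Phase I showed that only 5-10% of" falls happen in bathrooms. The documents do not support that step. It requires a video-only reading of 'detected' and no recovery through reports, families or records. The share of falls in common areas is not given either. Missed visits among controls would push the other way.

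A reader might also infer that ED visits are an invalid outcome because the system is meant to inform transfer (Purpose; Risk/Benefit Assessment). That goes too far. Avoiding an unneeded trip is an openly intended benefit, and hospitalization is less exposed to the transfer decision. The pilot totals do not show fewer EMS calls per fall: reductions of 37% in EMS use and 38% in falls give 0.63/0.62 = 1.02, and EMS use is not the same as ED transfer. The point here is one of wording.

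Lastly, Data analysis promises descriptive statistics for all variables. The sentence sits in the baseline text and specifies no comparison by arm, but for deaths, operations and ICU stays the gap is missing detail rather than a design fault.

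**Conclusion.** The missing contrast is established from the documents alone and needs no outside assumption: Hypothesis 3 has no specified analysis that can estimate its arm effect, and its outcome is defined in two ways. This should be corrected before analysis.

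The ascertainment point holds as a lack of specification. Fall finding, and the ED and hospital data tied to it, follow different routes by arm, and no section makes the common route the one that defines the count. It would be wrong to say that the plan does nothing about this, or to put a figure on the bias. The Aim 1 outcome definition, which uses incident reports in both arms, is not affected.

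The intervals in the working rest on assumed ED rates. They show only that a corrected comparison could be informative or inconclusive, depending on how many ED visits are fall-related and how overdispersed the counts are.

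**What to change.** 1. **Arm comparison.** For the 6-month controlled period, compare the number of ED visits and the number of hospitalizations per randomised resident by arm. Reuse the Aim 1 Poisson mixed model with an arm term, a facility effect, an offset for months observed and an allowance for overdispersion. Use counts in both sections.
2. **One count.** In both arms, define it from facility incident reports and the staff check, plus the enquiry to legal representatives (records release where needed), on the same schedule and whether or not a fall was detected. Events known only from the intervention arm's case review, or only from extra control-family calls, should not add to it.
3. **Predictor model.** Keep the regression on discovery and ground time as exploratory, within monitored periods.
4. **Reporting.** Tabulate deaths, operations and ICU stays by arm, descriptively. Describe a lower ED rate as reduced ED use.

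**Cost.** Protocol wording, one model and one table. Reading biweekly as every two weeks, the staff checks already planned for controls come to about 19 x 13 = 247 facility contacts, and the same contacts can cover intervention residents. That is a lower bound, because enrolment is staggered. Biweekly family calls in the intervention arm (up to 230 x 13 = 2,990) are not required; the enquiry to legal representatives need only be made at the same times in both arms. The downsides are that estimates may be imprecise, with no power stated for Aim 3, and that all-cause counts dilute an effect acting through falls.
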